**Procedures**

The proposed study is a prospective, single blind, two group randomized trial to test whether a timed activity intervention improves symptoms of CRD compared to an attention control condition and to investigate the mechanisms by which CRDs are influenced by a timed activity intervention. Interested CGs who contact the research team will be screened for eligibility by telephone. Those initially eligible and willing, will receive a clinician assessment to obtain written informed consent and to rule out primary sleep disorders requiring specialty care. Once eligibility is determined dyads will receive a baseline home interview (T1). Following the baseline interview, participants will be randomly assigned to experimental or attention-control group conditions and will be contacted to be informed of their respective group assignment within 48 hours of randomization. Experimental dyads will receive up to 8 contacts with a trained nurse interventionist over 1-month. The attention-control group dyads will receive comparable attention in a structured program involving the same number and mix of in-home and telephone contact as the treatment group. All dyads will be retested at 1-month from baseline (T2) to evaluate proximal outcomes of CRD symptoms, QoL, and CG sleep quality; and at 4 months to evaluate distal outcomes including QoL and other measures of satisfaction with the study procedures. Outcome measures will be assessed by interviewers masked to treatment assignment. Timed Activity Intervention Protocol: The timed activity group will involve 4 in-home visits in the mid morning and up to 4 brief telephone education sessions in the evening provided over 4 weeks. The timed activity intervention provides activities delivered at specific times in the daily cycle; it is theory-based, its components have been tested in pilot work; and it is portable and replicable (e.g., protocols are manualized). As in the pilot studies, the in-home sessions are spaced weekly so that the participants can have the opportunity to practice the activity with the interventionist and then on their own. During each session the interventionist will reinforce activity use, review problem solving approaches and provide education. In Session 1 (home visit), the interventionist will explain the nature of the visit and assess the health and functional status and preferences/interests of the PwAD. The interventionist will then provide a suggested morning activity that will match the functional capabilities and interests of the PwAD i.e., based on repetitive motion (e.g., folding towels; sorting objects) and integrating multi-sensory stimulation (photos of interest, objects pleasant to touch). Activities selected are simplified (1 to 2 steps vs. multiple, complex steps), to minimize errors. In Session 2 a follow up phone call will be provided on the following evening to provide coaching in the morning activity. In Session 3 (home visit) the interventionist will review the implementation of morning activities and provide training materials for the evening relaxation protocol. The evening relaxation protocol is a brief 10-step reflexology intervention in which pressure is applied to each of the reflex points on the feet for 30 seconds at a time for a total of 10 minutes. The protocol sequence is based on best practice guidelines. CG are provided a flip book and a CD-ROM demonstrating the procedure and developed in our pilot stud. In Sessions 4-5 (one home visit and one phone call), the interventionist will review integration of

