
morning and evening activities into daily schedule and will provide written instruction on environmental cues to promote activity and sleep. Session 6 (home visit) is a final review session and wrap up. Attention-Control Condition: The attention control group protocol will be delivered by trained RAs who will provide social attention, empathy and engagement similar in duration to that provided to the Timed Activity Intervention group. The length of time spent will be comparable to the length of time spent in the treatment arm, however this condition will contain no active elements beyond its nonspecific components, and no theoretical basis to support an effect on CRDs. The attention-control group will also involve 4 in-home visits in mid morning and up to 4 brief telephone education sessions in the evening. Each session is prescriptive and designed to maximize attention; yet, sessions will not involve any of the components of the timed planned activity (e.g. meaningful activities or relaxation). The attention control group will receive printed Alzheimers Association and NIH materials on home modification, health promotion/ talking to your doctor and advanced care planning that coincide with session content. In Session 1 (home visit), the attention control interventionist will explain the nature of the visit and provides information on home safety. In Sessions 2-3 (one home visit and one phone call) the interventionist will work together with CG to answer questions about home safety and review health promotion material. In Sessions 4-5 (one home visit and one phone call), the interventionist will provide and review information on advanced care planning. Session 6 is a wrap up and review provided in the home. Time with the attention-control RA will be documented on a tracking sheet for each session and signed by the CG. Bi-monthly supervisory sessions with attention-control RAs will involve case presentations to track content of the attention-control sessions. In our previous studies, we found that the attention-control intervention is well received and that participants fully participated in sessions. Treatment Implementation Monitoring: We have a well-defined oversight plan of treatment implementation in both treatment and attention control group arms using the NIH Behavior Change Consortium. To enhance fidelity, we incorporate their recommended strategies including use of treatment manuals, regular contact of PI with interventionists who present cases and discuss protocol issues, and on-going monitoring through direct observation of randomly selected sessions. We will address fidelity through training (using intervention manuals and separate interventionists for each condition), delivery (reminder calls to CGs the night before the intervention sessions, records of home sessions by date and duration, receipt (checklist completed by study team regarding intervention engagement) and enactment (demonstration by CG to interventionists). Feedback will be provided to each interventionist throughout the study period. We will quantitatively evaluate treatment delivery, including dose, intensity; and treatment receipt. Biweekly supervisory sessions will be held with treatment interventionists and control group interventionists separately. All project staff will undergo extensive training before they have contact with subjects. We will audiotape 10% of treatment and 10% of control group sessions. Audiotapes will be reviewed by the research team using monitoring checklists that evaluate quality of the session. Table 1 (uploaded) describes the variables to be measured their respective testing occasions and sources.

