### **Alternatives to Participation (optional)**

#### **Data and Safety Monitoring**

The PI will serve as the primary monitor for this study. Plan for reporting unanticipated problems or study deviations. The entire study team will be trained on immediately reporting any adverse events, alerts (e.g., hazardous or emergency situations), or study deviations to the PI. See Chart A (uploaded) for types of possible alerts that may be encountered and types of actions to be taken. If any serious possible or potentially study-related adverse events arise, the PI will notify to the IRB within 48 hours of learning of the events and will provide a safety report describing the adverse event and actions taken by the study. Additionally the PI will keep a log of adverse events in compliance with IRB policies and whether the event is unrelated, possibly related, or probably related to the study or intervention. Study deviations will be reported to the IRB when discovered along with any corrective actions taken by the study. Routine adverse events (such as non-intervention related events such as death) will be summarized for the IRB during the annual reviews. At the start of the study, participants and study partners will be instructed to report serious adverse events to the Coordinator who in turn will notify the PI. Serious adverse events, discovered either by the clinical team in routine activities or ones which the family report, will be presented to the PI together with the available data, and they will make a determination as to whether the event is unrelated, possibly related, or probably related to the study intervention. Because this is an evidence-based psychosocial intervention which seeks to provide care to meet the care needs of individuals with dementia living in the community, we do not anticipate adverse events beyond the background rate for this elderly population. Additionally, the aforementioned terms will be acknowledged if funding is received for a diversity supplement.

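### Adverse-event capture, in the text available, is passive and unstandardised: under-reporting is likely in both arms, and month-1 detection may differ by arm in an unknown direction

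*Combined protocol and SAP*

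**What the plan says.** All references are to the Combined protocol and SAP.

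**Data and Safety Monitoring** gives the capture rule: "Serious adverse events, discovered either by the clinical team in routine activities or ones which the family report, will be presented to the PI". The family's part in it is set once: "At the start of the study, participants and study partners will be instructed to report serious adverse events to the Coordinator". Staff have a wider duty: "The entire study team will be trained on immediately reporting any adverse events, alerts". The section also points to an attachment: "See Chart A (uploaded) for types of possible alerts that may be encountered and types of actions to be taken". The expectation is stated without a figure: "we do not anticipate adverse events beyond the background rate for this elderly population".

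**Procedures** sets who has routine contact in month 1. In the intervention arm, "Experimental dyads will receive up to 8 contacts with a trained nurse interventionist over 1-month". In the other arm, "The attention control group protocol will be delivered by trained RAs". The number and mix of home and telephone contacts are matched. All dyads are retested at 1 month (T2) and 4 months (T3) by masked interviewers. Table 1, said to list the variables and testing occasions, is also cited as uploaded.

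**Analysis Plan** contains no between-arm safety analysis.

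**The concern.** Passive capture finds the events that someone happens to notice or chooses to volunteer. Two consequences follow.

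The first is incompleteness. Families are asked to volunteer serious events only. A fall without admission or a minor injury therefore has no stated family route and depends on a staff member coming across it. Between T2 and T3 no session or visit is described, although T3 is meant to assess sustained uptake, so caregivers may still be using the activities then.

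The second is possible unequal detection in month 1. The staff who might come across an event differ between the arms in training and in what they talk about.

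At stake is how far safety counts by arm can be relied on when the trial is reported. The plan expects no excess over a background rate that it does not quantify, so a reader will naturally look to the control arm as the concurrent reference. The efficacy analyses are not affected.

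**Working it through.** The plan gives no event rate and no detection rate, so there is no stated figure to reproduce. The check sets the passages side by side and then illustrates the possible size.

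**1. Routes of capture (Data and Safety Monitoring; Procedures)**

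| Route | Events covered | When | Same in both arms? |
|---|---|---|---|
| Family report to the Coordinator | Serious only | Instructed once, at the start | Yes |
| Session staff | Any they come across | Month 1 | Number and mix of contacts yes; type of staff no |
| Masked T2 and T3 interviewers | Any they come across; no scripted question described | 1 and 4 months | Yes |

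Only the second row can produce a difference by arm through the observer.

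**2. Amount of contact.** Counting the sessions listed in Procedures: intervention 4 home + 2 telephone = 6; control 4 home + 2 telephone = 6. The quantity of contact is equal.

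**3. Gap.** T3 − T2 = 4 − 1 = 3 months, and 3/4 = 75% of each participant's follow-up. The gap is the same in both arms.

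**4. Equal under-detection.** Observed risk = true risk × detection. If detection is 60% in both arms (assumed), true risks of 10% and 10% appear as 6% and 6%, ratio 1.0. True risks of 20% v 10% appear as 12% v 6%: the ratio stays at 2.0, but the difference shrinks from 10 to 6 percentage points. Equal loss leaves the ratio unbiased and costs events.

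**5. Unequal detection in month 1 only.** Assumptions: equal true risk; a quarter of events fall in month 1; detection after month 1 is 60% in both arms; in month 1 one arm detects 90% and the other 80%, 70% or 50%.

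Overall detection = 0.25 × (month-1 detection) + 0.75 × 0.60.

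- 90%: 0.225 + 0.45 = 0.675
- 80%: 0.200 + 0.45 = 0.650; ratio 0.675/0.650 = 1.04
- 70%: 0.175 + 0.45 = 0.625; ratio 0.675/0.625 = 1.08
- 50%: 0.125 + 0.45 = 0.575; ratio 0.675/0.575 = 1.17

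If the nurse detects more, these are the false intervention-to-control ratios. If the research assistants detect more, the ratios invert to 0.96, 0.93 and 0.85 and would mask a small true excess. If detection is equal, the ratio is 1.0. On these figures 32.5% to 42.5% of events are missed (1 − 0.675 to 1 − 0.575), so incompleteness is the larger problem.

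**The case against.** The strongest reply is that the plan already guards against bias by arm. The contacts are matched in number and mix and similar in duration. The whole study team, which includes the research assistants and the masked interviewers, is trained to report any adverse event, not only serious ones. Families in both arms receive the same instruction, so a death or hospital admission need not wait for a nurse to find it. The study is classed as minimal risk, and no between-arm safety test is planned. All of this stands. It limits the problem but does not supply a standard question: a duty to report what one hears is not a procedure for asking.

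A reader might infer more than the documents support, in three ways.

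- *That the arms' safety data are not comparable.* The T2–T3 gap is identical in both arms and lowers completeness only. The difference in staff is a plausible source of unequal detection, not a demonstrated one. Nor is its direction known: a nurse may notice more, but the control sessions answer caregivers' questions about home safety, which could bring falls to light.
- *That the false risk ratio could be as high as 1.8.* That comes from applying an assumed 90% v 50% detection to all four months (0.90/0.50 = 1.80; against 80%, 0.90/0.80 = 1.1). Session staff are in contact for only one of those months.
- *That no other route exists.* Chart A and Table 1 are not in the text. If Table 1 already lists a safety item at T2 and T3, a cross-reference would settle the point.

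Worsening agitation is also partly covered, because neuropsychiatric symptoms are measured as an outcome.

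**Conclusion.** The concern holds in a limited form. As described in the text available, adverse-event capture is passive and unstandardised. Under-reporting is likely in both arms, especially between T2 and T3, and month-1 detection may differ by arm in an unknown direction.

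The size cannot be derived from the documents. The illustration gives an apparent ratio of 1.04 to 1.17, or its inverse, with no true difference. It rests wholly on assumed detection rates, on a quarter of events falling in month 1 and on equal detection afterwards. The documents do not show that the safety data are non-comparable. This is a weakness worth correcting because correction is cheap, and it does not undermine the trial.

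**What to change.** Add to Data and Safety Monitoring wording to this effect:

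> At T2 and at T3 the masked interviewer asks every caregiver the same short scripted questions about the period since the previous assessment: falls, injury, emergency visit, hospital admission, death. The questions follow the outcome measures and contain no prompt that points to either arm's content. Solicited events are tabulated by arm, with the number of dyads asked as denominator. Events found by interventionists or volunteered by families are listed separately by source. Immediate reporting is unchanged.

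Prompts hinting at reflexology, such as foot soreness, should be left out. They would invite disclosure of the arm to interviewers who also assess neuropsychiatric symptoms, a primary outcome. If Table 1 already contains such a query, cite it here instead.

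**Cost.** A few minutes in each of two interviews that already take place, one form and a short amendment; the current modification already adds a questionnaire to the T3 call. There will be some recall error over the three months from T2 to T3. A small risk of unmasking remains, reduced by asking last. Dyads lost before T3 are not reached, and the plan allows for 22% attrition by 4 months.

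**Reach.** The form reports 170 of 200 enrolled, 0 in intervention and 35 in follow-up. Taking these counts as dyads, the T3 query can reach at most 35 of 170 (21%) if enrolment stops now, or 35 + 30 = 65 of 200 (33%) if the remaining 30 are enrolled. The T2 query can reach only those 30. Events for earlier participants should be labelled as passively collected and the limitation stated in the report.

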### **The following documents are currently attached to this item:**

*There are no documents attached for this item.*

#### **Risk / Benefit Assessment**

This is a minimal risk study with potential benefit to subject and society.

## **General Attachments**

### ***The following documents are currently attached to this item:***

**Cover Letter (summaryofchanges.pdf)**

**Questionnaires (covid-19questionnaire.pdf)**
